11.4.4.2 Investigator evaluation of laboratory samples

Central laboratory

Chemistry, haematology, urinalysis (if applicable), serology, and serum pregnancy tests will be analysed by a central laboratory which will provide results to the trial sites. The investigator must evaluate all results outside the reference range ('clinically significant' or 'not clinically significant') and sign and date the report for documentation of the review. The signed and dated version will be filed with the investigator's trial documentation. Clinically significant abnormal tests must be repeated as soon as possible to confirm the abnormality. Subjects with clinically significant abnormal test results should be followed up at the discretion of the investigator.

If a screening laboratory result is abnormal and of clinical significance, it will be at the investigator's discretion to decide if the subject should be randomised into the trial. However, subjects meeting exclusion criterion no.16 (laboratory abnormalities) must not be randomised into the trial.

A laboratory manual will be provided to the trial sites specifying the procedures for collection, processing, storage, and shipment of samples, as well as laboratory contact information specific to this trial.

Tests performed at the trial site

Urine samples will be tested with a dipstick according to the schedule of trial procedures (Section 4). If a dipstick shows any abnormal reading, a urine sample must always be collected and sent to the central laboratory for further analysis, regardless of causality or investigator's assessment of significance.

Women of childbearing potential will have a urine pregnancy test performed at the trial site at baseline prior to randomisation. The test will be repeated every 4 weeks as shown in the schedule of trial procedures in Section 4.

THIS DOCUMENT CONTAINS CONFIDENTIAL INFORMATION AND MUST NOT BE COPIED OR MADE AVAILABLE TO ANY THIRD PARTY WITHOUT THE PRIOR WRITTEN CONSENT OF THE LEO PHARMA GROUP

Reporting in eCRF

At each visit where samples must be taken, the site staff will record in the eCRF if a sample (urine/blood) was taken and the investigator's assessment of the results ('normal', 'abnormal, not clinically significant', 'abnormal, clinically significant').

It will be recorded in the eCRF if the subject is a woman of childbearing potential and if a urine pregnancy test was performed, if not, a reason should be provided. Also, the date and the outcome of the urine pregnancy test will be recorded in the eCRF ('positive', 'negative').

Clinically significant abnormal laboratory results at the screening visit will be documented as medical history in the eCRF. At subsequent visits, any clinically significant deterioration of a pre-existing condition will be reported as an AE. Any new clinically significant abnormal laboratory values, sign, symptom, or illness occurring after randomisation will be reported as an AE in accordance with Section 13.3.

11.5 Other assessments: Patient-reported outcomes

11.5.1 Overview

The C-SSRS must be completed after all other assessments have been performed at the trial visit, but prior to IMP administration. The investigator should not question the subject's answers. The investigator must review the data for eligibility (at screening and at baseline), timeliness, and completeness, and take appropriate action (see below) before the subject leaves the trial site.

11.5.2 Columbia-Suicide Severity Rating Scale

The C-SSRS is a rater-administered, standardised, and validated instrument developed for the assessment of the severity and frequency of SIB (26, 27).

The C-SSRS is divided into suicidal ideation (category 1 to 5), suicidal behaviour (category 6 to 9), completed suicide (category 10), and non-suicidal self-injurious behaviour:

Suicidal ideation

- Category 1: Wish to be dead.
- Category 2: Non-specific active suicidal thoughts.
- Category 3: Active suicidal ideation with any methods (not plan) without intent to act.
- Category 4: Active suicidal ideation with some intent to act, without specific plan.

THIS DOCUMENT CONTAINS CONFIDENTIAL INFORMATION AND MUST NOT BE COPIED OR MADE AVAILABLE TO ANY THIRD PARTY WITHOUT THE PRIOR WRITTEN CONSENT OF THE LEO PHARMA GROUP

- Category 5: Active suicidal ideation with specific plan and intent.

Suicidal behaviour

- Category 6: Preparatory acts or behaviour.
- Category 7: Aborted attempts.
- Category 8: Interrupted attempts.
- Category 9: Actual attempts (non-fatal).

Completed suicide

- Category 10: Completed suicide.

Non-suicidal self-injurious behaviour

- Non-suicidal self-injurious behaviours.

At all visits where the C-SSRS interview must be performed (see Section 4), it must be done after all other visit activities have been completed. However, the C-SSRS interview must be performed and the answers reviewed before the IMP administration. The C-SSRS takes approximately 3 to 10 minutes to complete.

The investigator must evaluate the subject's eligibility in relation to exclusion criteria no. 11 and 12 for the C-SSRS components 'history of suicidal behaviour' and 'suicidal ideation' at screening (Visit 1) and baseline (Visit 2; Week 0).

The 'baseline' paper version of the C-SRSS will be used at screening and the 'since last visit' paper version will be used at all subsequent visits. The C-SSRS assessments will be transcribed into the eCRF.

Subjects with suicidal ideation of category 4 or 5 or any suicidal behaviour must be referred to a mental health professional and be discontinued from IMP. In addition, the event must be reported as an AE.

11.5.3 Patient Health Questionnaire-8

The PHQ-8 is a validated and widely used 8-item version of the Patient Health Questionnaire depression scale designed to clinically assess subjects for symptoms and signs of depression (16).

THIS DOCUMENT CONTAINS CONFIDENTIAL INFORMATION AND MUST NOT BE COPIED OR MADE AVAILABLE TO ANY THIRD PARTY WITHOUT THE PRIOR WRITTEN CONSENT OF THE LEO PHARMA GROUP

At all visits where the PHQ-8 must be completed (see Section 4), the answers must be reviewed by the investigator before the IMP administration. The PHQ-8 questionnaire will be filled out on a separate device and takes approximately 3 minutes to complete.

For PHQ-8 scores ≥ 10 , the subject must be referred to a mental health professional (score ≥ 10 is cut-point for defining current depression), and the event must be reported as an AE (16). Subjects scoring ≥ 15 must in addition be discontinued from IMP.

11.6 End of trial

Both an end-of-treatment form and an end-of-trial form will be completed in the eCRF for all randomised subjects.

11.6.1 End-of-treatment form

An end-of-treatment form will be completed in the eCRF for all randomised subjects when they have had their last administration of IMP. This form will also be completed for subjects who permanently discontinue IMP and subjects who withdraw from trial (see Section 10.3 for early termination assessments).

It will be recorded on the end-of-treatment form if the subject completed the treatment. If not, the primary reason for permanent discontinuation of IMP must be recorded (see Section 10.2.1).

11.6.2 End-of-trial form

An end-of-trial form must be completed in the eCRF for all randomised subjects. The following data will be collected:

- Did the subject complete the trial. If not, the primary reason for early termination must be recorded.
- Date of last contact.
- Primary reason for withdrawal from trial (lack of efficacy, adverse event, withdrawal by subject, lost to follow-up, death, pregnancy, other). ‘Lack of efficacy’ should be assigned when a subject experiences aggravation/exacerbation/worsening of the trial disease, even when it is documented as an (S)AE according to Section 13.6.5. If ‘other’ is selected, a specification must be provided in the eCRF.

The end-of-trial form will be completed when the subject has had his/her last visit (that is, the final visit at Week 28, or earlier in case of early termination [see Section 10]).

THIS DOCUMENT CONTAINS CONFIDENTIAL INFORMATION AND MUST NOT BE COPIED OR MADE AVAILABLE TO ANY THIRD PARTY WITHOUT THE PRIOR WRITTEN CONSENT OF THE LEO PHARMA GROUP

11.7 Estimate of total blood volume collected

Blood samples will be drawn for haematology, biochemistry, and serology. The total volume of blood to be drawn is approximately 60 mL, which is significantly less than the total volume of blood drawn during a blood donation (approximately 500 mL).

11.8 Storage of biological samples

Blood and urine samples are collected only for clinical laboratory tests in the trial (haematology, biochemistry, serology, and urinalysis). The storage of these biological samples will therefore follow the standard operating procedures at the sites and laboratories where the tests are conducted. Typically, samples are stored for no more than a few days after sample collection.

THIS DOCUMENT CONTAINS CONFIDENTIAL INFORMATION AND MUST NOT BE COPIED OR MADE AVAILABLE TO ANY THIRD PARTY WITHOUT THE PRIOR WRITTEN CONSENT OF THE LEO PHARMA GROUP

12 Scientific rationale for trial design and appropriateness of assessments

12.1 Scientific rationale for trial design

This is a phase 4, randomised, blinded (subject and assessor), parallel-group, multi-site, clinical trial. The parallel-group design is chosen as it is the only appropriate design to evaluate the trial objectives. Furthermore, randomisation provides the most reliable method removing selection bias between 2 groups of subjects. Additionally, the randomisation will be stratified by body weight to further ensure comparability of the treatment groups. The subjects and the assessors will be blinded, as it is the only design that can provide strong clinical evidence compared with the alternative designs, e.g. assessor-blinded only. Additionally, a blinded design is also expected to be a requirement from regulatory authorities.

The duration of the trial is approximately 32 weeks including a screening period of 2 to 4 weeks, and the primary endpoint is assessed at Week 16, ensuring a treatment duration long enough for efficacy and safety evaluations for both treatments during the induction period. Moreover, from the clinical perspective, it is also important to investigate if the treatment differences are sustained for a longer period. Therefore, an additional 12 weeks of active treatment are included, resulting in a total of 28 weeks of therapy, providing enough time to evaluate if efficacy is sustained for both treatments.

The eligible trial population is described in detail in Section 8. Most criteria are defined according to the approved IB of Kyntheum® and EU SmPC of Tremfya®. Inadequate response to ustekinumab is defined as IGA ≥ 2 after at least 3 doses at or higher than the approved dose or frequency, and this correlates well with the currently acceptable treatment goals.

This trial will provide a direct comparison of brodalumab and guselkumab on regimens according to the approved IB/SmPC. The data generated could support evidence-based decisions on sequencing and switching biologic treatments within psoriasis in the clinical setting.

12.2 Appropriateness of assessments

12.2.1 Rationale for primary endpoint

PASI is the most thoroughly validated and the most extensively studied psoriasis clinical severity scoring tool, which assesses the extent of psoriasis at 4 anatomical regions with the signs of erythema, scale, and elevation (28). The efficacy endpoint, PASI 75, together with static Physician's Global Assessment (sPGA) score of 1 or 0, are recommended by the European Medicines Agency (EMA) for assessment of clinical efficacy (29) and recognised

THIS DOCUMENT CONTAINS CONFIDENTIAL INFORMATION AND MUST NOT BE COPIED OR MADE AVAILABLE TO ANY THIRD PARTY WITHOUT THE PRIOR WRITTEN CONSENT OF THE LEO PHARMA GROUP

as important endpoints in clinical trials in psoriasis by regulatory authorities in the EU. However, with more effective treatments emerging, patients and physicians are increasingly looking for more ambitious response parameters. As this trial aims to compare 2 highly efficacious drugs, it is considered that PASI 100 is the most reliable and relevant response criterion to identify the differences in efficacy among the 2 treatments.

12.2.2 Rationale for assessment of palmoplantar psoriasis

Palmoplantar psoriasis is a variant of plaque psoriasis that develops on the palms and soles. It can be seen with or without psoriasis elsewhere on the body and affects approximately 3–4% of all psoriasis patients (30, 31).

Treatment for palmoplantar psoriasis is often challenging, as the thick epidermal layers of the palms and soles prevent local action of topical treatments (32). However, randomised controlled trials on the efficacy and safety of biologics for treatment of palmoplantar psoriasis are still limited, because palmoplantar psoriasis patients usually do not have sufficiently high BSA involvement to meet the inclusion criteria (32-34).

Less than 5% BSA is involved in palmoplantar psoriasis without involvement of other body areas. Despite this relatively small BSA involvement, subjects with palmoplantar psoriasis suffer from substantial impairment of health-related quality of life, having difficulty with daily activities involving hands and feet (34, 35).

Therefore, palmoplantar psoriasis is a disease with significant quality-of-life issues, where more data from clinical trials are needed. The psoriasis patients with predominantly hands and/or feet involvement are able to participate in this trial due to lack of a BSA inclusion criterion. Hence, the PP-IGA and PP-PASI are included in this trial, as they are validated, reliable, and responsive assessments of palmoplantar psoriasis, which have been used in previous clinical trials (36-38).

12.2.3 Rationale for assessment of genital psoriasis

Traditionally, the genitals have been acknowledged as a vulnerable and difficult-to-treat area with topicals. Thus, there is an unmet need for effective and proven treatments of genital psoriasis.

Questionnaire-based studies have shown a high prevalence of genital psoriasis among patients with plaque psoriasis (28.6–46%) (39, 40). A clinical observational study showed that the current prevalence of genital psoriasis was 38% and the lifetime prevalence of genital psoriasis was as high as 63% (41). While psoriasis in the genital area is often overlooked and

THIS DOCUMENT CONTAINS CONFIDENTIAL INFORMATION AND MUST NOT BE COPIED OR MADE AVAILABLE TO ANY THIRD PARTY WITHOUT THE PRIOR WRITTEN CONSENT OF THE LEO PHARMA GROUP

left untreated, it has been shown to have a significant impact on health-related quality of life and it is associated with a high disease burden (42).

Previous tools for assessing genital psoriasis have not been widely accepted or used in clinical trials or in clinical practice. Recently, the sPGA-G was developed and validated for the assessment of genital psoriasis in clinical trials (23, 43). The tool has been accepted by the United States Food and Drug Administration (FDA).

Taken together, genital psoriasis is an important and often overlooked manifestation of psoriasis in which data from clinical trials are needed. The sPGA-G is considered a relevant and feasible tool for the assessment of genital psoriasis and is therefore included as a clinical assessment in this trial.

THIS DOCUMENT CONTAINS CONFIDENTIAL INFORMATION AND MUST NOT BE COPIED OR MADE AVAILABLE TO ANY THIRD PARTY WITHOUT THE PRIOR WRITTEN CONSENT OF THE LEO PHARMA GROUP

13 Adverse events

13.1 Definition and classification of adverse events

AEs and SAEs are defined in [Appendix 1](#).

Classification of AEs in terms of severity, causality, and outcome is defined in [Appendix 2](#). Causality assessment will be made for all IMPs (brodalumab, guselkumab, and dummies).

13.2 Collection of adverse event reports

AE data must be collected from time of first trial-related activity after the subject has signed the ICF until completion of the clinical trial (Section [7.3](#)).

AEs must be assessed by medically qualified personnel.

At all visits, the subject will be asked a non-leading question by the investigator about AEs, for example: “How have you felt since I saw you last?” No specific symptoms should be asked for. It is important that the investigator also observes the subject for any changes not reported by the subject and records these changes.

Refer to Sections [11.4.1](#) to [11.4.4](#) for principles of data entry in the eCRF with regard to vital signs and laboratory results (e.g. abnormal findings).

13.3 Reporting of adverse events

AEs reported by the subject or observed by the investigator must be recorded on the AE form of the eCRF and should be described in the following manner:

The *AE term* must be in precise English medical terminology (that is, not necessarily the exact words used by the subject). Whenever possible, a specific diagnosis should be stated (for example ‘allergic contact dermatitis’).

The *duration* of the AE must be reported by the start date and stop date of the event (if the event is ongoing, it will also be recorded). In addition, it will be recorded if the AE started prior to first administration of IMP.

AEs must be classified in terms of severity, causality, and outcome according to the definitions in [Appendix 2](#).

THIS DOCUMENT CONTAINS CONFIDENTIAL INFORMATION AND MUST NOT BE COPIED OR MADE AVAILABLE TO ANY THIRD PARTY WITHOUT THE PRIOR WRITTEN CONSENT OF THE LEO PHARMA GROUP

Action taken with IMP: any action taken with IMP as a consequence of the AE must be recorded (dose not changed, temporary discontinuation of IMP, permanent discontinuation of IMP, not applicable, unknown).

Other action taken: any other action taken as a result of the AE must be recorded (none, concomitant medication, concurrent procedure).

Withdrawn from trial due to this AE: it must be recorded whether the AE led to withdrawal from the trial.

13.4 Reporting of serious adverse events

The criteria that define an AE as serious (that is, an SAE) are defined in [Appendix 1](#). SAE criteria are also listed on the SAE form.

13.4.1 Investigator reporting responsibilities

Any SAE must be reported to LEO Pharma on the (paper) SAE form within 24 hours of first knowledge. This report should contain an assessment of available information on seriousness, severity, causal relationship to the IMPs, device, or trial procedure, the action taken, the outcome to date, and a narrative description of the course of the event.

By signing and dating the SAE form, the investigator acknowledges that he/she is aware of the SAE and has assessed the causal relationship of the IMP(s) and any of the other medications to the SAE.

The actual reporter, if not the investigator, should also sign and date the SAE report.

The completed SAE form must be faxed or scanned and e-mailed to Global Safety at LEO Pharma using the e-mail address or fax number below:

Global Safety at LEO Pharma

E-mail address: [contact]

[contact]

If relevant, the investigator will enclose other information with the SAE form, such as anonymised reports of diagnostic procedures, hospital records, autopsy reports, etc.

THIS DOCUMENT CONTAINS CONFIDENTIAL INFORMATION AND MUST NOT BE COPIED OR MADE AVAILABLE TO ANY THIRD PARTY WITHOUT THE PRIOR WRITTEN CONSENT OF THE LEO PHARMA GROUP

Additionally, Global Safety at LEO Pharma may request further information to fully assess the SAE. The investigator must forward such information to LEO Pharma upon request by fax or e-mail (see contact details above).

The investigator must notify the local IEC(s) of SAEs, as required by current applicable legislation for the concerned country.

SAEs occurring after the completion of the clinical trial should not be routinely sought or recorded. However, such events should be reported to Global Safety at LEO Pharma (see contact details above) if the investigator becomes aware of them.

13.4.2 LEO Pharma reporting responsibilities

Global Safety at LEO Pharma is responsible for assessing whether or not an SAE is expected. The relevant reference safety information documents for this clinical trial are:

- For brodalumab, the IB Section 7.2, edition 13.0 and subsequent updates must be used.
- For Tremfya® (guselkumab) the current SmPC in the EU must be used.

Global Safety at LEO Pharma will notify the regulatory authorities and concerned investigators of SAEs according to the current applicable legislation for the concerned countries.

The IEC(s) will be notified of SAEs according to the current applicable legislation for the concerned countries.

All SAEs which are assessed as causally related to the IMP(s) by either the investigator or LEO Pharma (44), and which are unexpected (Suspected, Unexpected Serious Adverse Reactions [SUSARs]), are subject to expedited reporting to regulatory authorities and IEC(s) according to the current applicable legislation in the concerned countries. Investigators will be notified of the evolving safety profile of the IMP on an ongoing basis.

13.5 Other events that require expedited reporting

13.5.1 Pregnancy

Any pregnancy occurring after first exposure to IMP and until the subject has completed the trial must be reported to LEO Pharma within 24 hours of first knowledge using the (paper) pregnancy form (part I). All pregnancies must be followed up until delivery or termination

THIS DOCUMENT CONTAINS CONFIDENTIAL INFORMATION AND MUST NOT BE COPIED OR MADE AVAILABLE TO ANY THIRD PARTY WITHOUT THE PRIOR WRITTEN CONSENT OF THE LEO PHARMA GROUP

and final outcome must be reported on the (paper) pregnancy form (part II) within 24 hours of first knowledge.

The completed pregnancy forms must be faxed or scanned and e-mailed to Global Safety at LEO Pharma. Contact details are given in Section [13.4.1](#).

Pregnant subjects must immediately discontinue IMP permanently (Sections [10.2.1](#) and [10.3](#)).

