5.4 Ethical considerations

This trial will be conducted in accordance with the ethical principles that have their origins in International Council for Harmonisation Good Clinical Practice (ICH GCP) guidelines in compliance with the approved protocol and applicable regulatory requirements.

In accordance with the current version of ICH GCP guidelines, qualified medical personnel employed by LEO Pharma will be readily available to advise on trial-related medical questions. Medical monitoring will be performed throughout the trial.

In this trial, all subjects will be treated with biologic medications approved in EU for the treatment of moderate-to-severe plaque psoriasis. Since the trial has no placebo arm, any ethical considerations regarding withholdment of treatment do not apply.

No children or other vulnerable subjects incapable of giving informed consent will be included in this clinical trial. Pregnant or breastfeeding women and women trying to conceive will not be included in the trial. Women of childbearing potential must agree to use a highly effective method of contraception to prevent pregnancy during the clinical trial and until 12 weeks after discontinuation of treatment with investigational medicinal product (IMP). In addition, all women of childbearing potential will have a pregnancy test performed before, during, and after trial procedures to minimise the risk of foetuses being exposed to the IMPs.

Suicidal ideation and behaviour (SIB), including completed suicide, have been reported in patients treated with brodalumab. The majority of patients with suicidal behaviour had a history of depression and/or suicidal ideation or behaviour. A causal association between treatment with brodalumab and increased risk of SIB has not been established (14).

Since a history of prior depression and/or SIB are known risk factors for new SIB events (15), subjects with a recent history of depression (within 2 years), Patient Health Questionnaire-8

THIS DOCUMENT CONTAINS CONFIDENTIAL INFORMATION AND MUST NOT BE COPIED OR MADE AVAILABLE TO ANY THIRD PARTY WITHOUT THE PRIOR WRITTEN CONSENT OF THE LEO PHARMA GROUP

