- Guselkumab 100 mg (1.0 ml) subcutaneously at Weeks 0, 4, and then Q8W until the end of trial (last administration of guselkumab at Week 20).
- Dummy 2 (placebo 1.5 ml) subcutaneously at Weeks 0, 1, 2, and then Q2W until the end of trial (last administration of dummy 2 at Week 26).

The primary endpoint will be assessed at Week 16.

Maintenance period (Week 16 to Week 28)

The subjects will follow the treatment regimen described above. Last injections (brodalumab in Arm 1 and dummy 2 injection in Arm 2) will be given at Week 26. The subjects and assessors will be blinded throughout the trial.

Baseline, efficacy, and safety assessments during the trial are described in Section 11.

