8.2 Inclusion criteria

For inclusion into this trial, subjects must fulfil all of the following criteria:

1. Signed and dated informed consent has been obtained prior to any protocol-related procedures.
2. Subject is ≥ 18 years of age at the time of screening.
3. Subject has a diagnosis of plaque psoriasis for at least 6 months before the first administration of IMP as determined by the investigator.
4. Subject has inadequately controlled plaque psoriasis currently treated with ustekinumab, and fulfils ALL of the following criteria:
 - Ustekinumab administered at least 3 times at or higher than the approved dose or frequency before randomisation (Stelara® SmPC) (17).
 - Investigator's Global Assessment (IGA) ≥ 2 at screening and baseline.
 - Absolute PASI >3 at screening and baseline.
5. Subject has no evidence of active tuberculosis according to local standard of care for patients requiring initiation of a biologic treatment. Subjects with adequately treated latent tuberculosis, according to local guidelines, are eligible.
 - a. A tuberculosis test can be performed at the central laboratory.

THIS DOCUMENT CONTAINS CONFIDENTIAL INFORMATION AND MUST NOT BE COPIED OR MADE AVAILABLE TO ANY THIRD PARTY WITHOUT THE PRIOR WRITTEN CONSENT OF THE LEO PHARMA GROUP

- b. If a local laboratory test is performed to confirm this criterium, the local laboratory should be assessed before the local testing is performed.
6. Subject who is a woman of childbearing potential* must have a negative serum pregnancy test at screening and a negative urine pregnancy test at baseline.

* A woman is defined as being of childbearing potential if she is not postmenopausal (at least 12 months with no menses without an alternative medical cause prior to screening) and not surgically sterile (hysterectomy, bilateral salpingectomy, or bilateral oophorectomy).

7. Subject who is a woman of childbearing potential* must use a highly effective** form of birth control throughout the trial and at least for 12 weeks after last administration of IMP.

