5.2 Extent of exposure

Exposure will be summarised based on the SAF. For each treatment group, the summary will include the total patient years of exposure, the total patient weeks of exposure and the exposure time, based on the categories ‘< 16 weeks’, ‘16-24 weeks’, and ‘> 24 weeks’. For each treatment group, the summary will also include the total patient years of observation, beginning from the date of randomisation and ending at the date of last contact. Subjects will be considered exposed to IMP within 5 half-lives after the most recent date of IMP administration with half-lives assumed to be as described in [Panel 8](#). Exposure time will be truncated at the end of observation, i.e. at the date of last contact.

Panel 8. Assumed half-lives for investigational medicinal products

IMP	Assumed half-life	Rationale for assumption
Brodalumab Trade name: Kyntheum®	10.9 days	According to (1), “(...) the estimated half-life of brodalumab was 10.9 days at steady-state after every other week subcutaneous dose of 210 mg”
Guselkumab Trade name: Tremfya®	16.5 days	According to (2), “Mean half-life ($T_{1/2}$) of guselkumab was approximately 17 days in healthy subjects and approximately 15 to 18 days in patients with plaque psoriasis across studies”. Based on this, the average of 15 days and 18 days will be the assumed half-life.
Placebo 1.0 mL (dummy 1 to mimic guselkumab)	0.0 days	According to the CTP Panel 6, “The placebo solution (...) does not contain any active substance”.
Placebo 1.5 mL (dummy 2 to mimic brodalumab)	0.0 days	According to the CTP Panel 6, “The placebo solution (...) does not contain any active substance”.

Abbreviations: CTP = clinical trial protocol; IMP = investigational medicinal product. **Notes:** The described IMPs refer to those identified in CTP Panel 6.

THIS DOCUMENT CONTAINS CONFIDENTIAL INFORMATION AND MUST NOT BE COPIED OR MADE AVAILABLE TO ANY THIRD PARTY WITHOUT THE PRIOR WRITTEN CONSENT OF THE LEO PHARMA GROUP

The cumulated number of doses administered to each subject will be determined and summarised descriptively. The same summarisation will be done for the cumulated number of active doses administered to each subject. For subjects who withdraw from the trial, are lost to follow-up, or permanently discontinue IMP, their cumulated number of doses will be calculated up until the time of withdrawal/loss to follow-up/permanent discontinuation of IMP.

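### Pregnancy reporting ends at trial completion (Week 28) while contraception is required until 12 weeks after the last IMP; pregnancies that begin in between need not be reported

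*Protocol*

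**What the plan says.** Protocol Section 13.5.1 sets the reporting rule. A pregnancy that arises once IMP has been given and "until the subject has completed the trial must be reported to LEO Pharma within 24 hours"; the clock starts when the site first learns of it. Pregnancies within that window are followed to delivery or termination. Section 7.3 defines completion as having concluded all trial periods, and the last period listed in Section 7.1 ends at Week 28, with no follow-up period after it. The last scheduled pregnancy test in Panel 3 is also at Week 28.

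Inclusion criterion 7 (Section 8.2) requires women of childbearing potential to use highly effective contraception "throughout the trial and at least for 12 weeks after last administration of IMP". Section 5.4 also sets 12 weeks, counted from discontinuation of IMP.

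On dosing, Section 7.1 states: "Last injections (brodalumab in Arm 1 and dummy 2 injection in Arm 2) will be given at Week 26". For the active drug in Arm 2 it gives "last administration of guselkumab at Week 20". Section 13.1 and Panel 6 count the dummies as IMPs.

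For events after the trial, Section 13.4.1 says that SAEs are not to be sought routinely but should be reported if the investigator learns of them. Section 13.5.1 has no matching sentence for pregnancy.

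**The concern.** The protocol asks women to avoid pregnancy for a stated period after the last IMP, but its duty to report a pregnancy can lapse before that period is over. A woman who completes treatment, leaves at Week 28 and conceives in the following weeks is still inside the contraception period, yet the site has no instruction to report the pregnancy or follow it to outcome, even if she telephones to say so.

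What would be lost is safety information on pregnancies that begin soon after the last dose, including the uneventful ones needed to interpret any adverse outcome. No efficacy analysis or sample-size figure depends on this. The length of the contraception period is not questioned here; the issue is that the sections do not match.

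**Working it through.** The plan gives no figure of its own for this gap, so there is none to reproduce. The check is timeline arithmetic.

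Inputs:
- End of reporting E = Week 28 (Protocol 13.5.1 with 7.3 and 7.1).
- Contraception period W = 12 weeks (Protocol 8.2, criterion 7; Section 5.4).
- Last dose L = Week 26 for any IMP in either arm, or Week 20 for the last active guselkumab dose (Protocol 7.1).
- Visit windows of ±3 days at Weeks 26 and 28 (Panel 3).
- Half-lives of 10.9 days for brodalumab, 16.5 days for guselkumab and 0.0 days for the dummies (SAP Panel 8).

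Covered weeks = E − L. Uncovered weeks = W − (E − L) = L − 16, and never below zero.

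| Counted from | Period ends (L + 12) | Covered | Uncovered |
|---|---|---|---|
| Last IMP, Week 26 | Week 38 | 2 weeks | 10 of 12 (83%) |
| Last active guselkumab, Week 20 | Week 32 | 8 weeks | 4 of 12 (33%) |
| Last IMP at Week 16, subject stays to Week 28 | Week 28 | 12 weeks | 0 of 12 |

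Visit windows: the 14 days between the Week 26 and Week 28 visits can be as few as 14 − 6 = 8 or as many as 14 + 6 = 20. Out of 84 days, the uncovered share then runs from (84 − 20)/84 = 76% to (84 − 8)/84 = 90%.

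For comparison, five half-lives after the last active dose:
- Brodalumab: 5 × 10.9 = 54.5 days = 7.8 weeks; 26 + 7.8 = Week 33.8. The part after Week 28 is 54.5 − 14 = 40.5 days (74%).
- Guselkumab: 5 × 16.5 = 82.5 days = 11.8 weeks; 20 + 11.8 = Week 31.8. The part after Week 28 is 82.5 − 56 = 26.5 days (32%).

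These two dates are extrapolations from the half-lives. They are not exposure times that the SAP would report.

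Check of two possible remedies for a subject who stops IMP at Week 4 and stays to Week 28. A window ending 12 weeks after the last IMP would close at 4 + 12 = Week 16, which is 12 weeks earlier than the present text. A window ending at the later of completion and 12 weeks after the last IMP closes at max(28, 16) = Week 28, so nothing is lost. For a subject who completes treatment it closes at max(28, 38) = Week 38.

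**The case against.** The case for leaving the text alone has several parts.

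- Stopping at completion matches AE collection in Section 13.2, so it may be deliberate. This is fair, but Section 13.4.1 adds a route for SAEs learned of later, and the documents give no reason why pregnancy has none.
- Serious outcomes do have a route. A congenital anomaly is an SAE criterion (Appendix 1), SAEs learned of after completion should be reported (13.4.1), and SAE follow-up may go beyond the end of the trial (13.7). This stands in part: adverse outcomes may arrive that way, but not the pregnancies without an SAE.
- A pregnancy that begins before completion and is discovered later is still reportable under 13.5.1. This stands. The gap concerns only pregnancies that begin after completion.
- A reader might infer that women conceive while still exposed by the SAP's definition, because SAP Section 5.2 says "Subjects will be considered exposed to IMP within 5 half-lives after the most recent date of IMP administration". The documents do not support that as stated. The same section truncates exposure time at the date of last contact, and it defines exposure for summary tables, not a period of foetal risk.
- The number of women affected is probably small. The documents do not give it, and SAP Section 6 records a decision to end the trial ahead of schedule. This limits the importance of the point but does not reconcile the sections.

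**Conclusion.** The mismatch between Section 13.5.1 on the one hand and criterion 7 and Section 5.4 on the other is real, and inexpensive to remove. For a subject who completes treatment on schedule, 10 of the 12 weeks after the last IMP fall outside the reporting window. That figure follows the protocol's own wording, in which dummies are IMPs.

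A reader might infer that most of a post-dose risk period goes unmonitored in both arms. The documents do not support that. In the guselkumab arm the Week 26 injection is a dummy, and 4 of 12 weeks are uncovered when counted from the last active dose. Subjects who stop IMP early and stay to Week 28 have more of the period covered, and all of it if the last IMP was at Week 16 or earlier. Nor does the protocol call the 12 weeks a risk period: criterion 7 states a contraception requirement, and the remark in Section 5.4 about foetal exposure is attached to pregnancy testing.

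The result assumes that completion means Week 28 and that doses are given as scheduled. It is a modest gap in safety reporting.

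**What to change.** Reconcile Section 13.5.1 with criterion 7 and Section 5.4. Keep the start at first exposure to IMP, and let the window end when the subject has completed the trial or 12 weeks after the last administration of IMP, whichever is later. The later-of form matters, because a plain 12-week limit would shorten reporting for those who stop IMP before Week 16 and stay. It also gives a usable end date for a woman who withdraws and so never completes in the sense of Section 7.3. At the last visit, ask subjects to tell the site of any pregnancy within that period.

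The cost is a sentence in the protocol and one in the subject information, with no added visit or test and no change to any planned analysis. The downside is that sites accept spontaneous reports for up to 10 more weeks (38 − 28) and must follow each reported pregnancy to outcome. That follow-up may run past the site closure described in Appendix 3I, so the sponsor should say who carries it on.
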